### **Involvement of Human Subjects**

Children and adults (male/female;  $\geq$ 8 y.o.), including healthy controls and individuals with SPI, will be recruited.

*Sex considerations*: Even though some SPI have a sex preference – as for example the prevalence of people who sustain spinal cord injuries is greater in males than females – we plan to recruit equal numbers of males and females to assess possible differences between men and women with regards to the expected outcomes of this work.

Age considerations: SPI affect both children and adult populations who may develop verbal communication impairments and require the need for AAC devices. We will therefore include children  $\geq$ 8 yo. who are able to spell, follow 2-3 step directions, have functional vision sufficient to read point text, and have a motor impairment that requires the use of AAC technology.

*Racial/Ethnic origin considerations:* We plan to recruit a subject population that includes equal participation of minorities and is representative of the racial and ethnic diversity of the greater Boston and Lincoln areas.

*Other considerations:* Subjects must speak English so that we can accurately develop an AAC keyboard interface and speech model based on English-language and must be literate in English so that they can read speech task prompts from a computer monitor.

*Recording apparatus:* All sensors used in this study will be non-invasive and electrically isolated for subject safety. A Trigno Avanti https://www.delsys.com/trigno/research/ wireless data acquisition system (Delsys Inc., Natick, MA) designed for detecting both sEMG and IMU signals from the same sensor will be located on the subject's forehead for these experiments. The sensor wirelessly communicates with either a Trigno Base station or a Tablet. Signals from the sensors will be sampled at 2000 samples/sec using EMGWorks software (Delsys Inc., Natick, MA), and interfaced over USB to a PC workstation for post processing. The sensor will be secured to the skin using a disposable medical-grade double-sided interface.

*Sensor locations:* The skin area of each sensor location will be prepared using alcohol wipes to cleanse the skin surface and repeated tape peels to remove possible superficial contaminants (oil; dead skin) so as to improve signal quality. Facial hair may be shaved with the subjects' permission using a disposable safety razor in the immediate area of the sensor recording sites. We anticipate placement of no more than 1 sensor at any one time, with the IMU body placed on the participant's forehead and the sEMG mini-head placed adjacent to the eye to record muscle activations from either blinking or raising the eyebrow.

## Inclusion/Exclusion Criteria

# INDIVIDUALS WITH SPI

Inclusion criteria:

- Adults or Children; age> 8 y.o.

- Male or Female.

- All participants will be: (a) able to spell, (b) able to follow 2-3 step directions, (c) have functional vision sufficient to read 40 point text, and (d) have a motor impairment that requires the use of an alternative access strategy to communicate and/or use technology.

- Current or prospective AAC user with complex communication needs representing a broad spectrum of developmental and acquired SPI disabilities resulting from high spinal cord injury,

chronic Guillain-Barré syndrome, brain stem stroke, cerebral palsy, locked-in syndrome, among others

- Sufficient head control and voluntary facial muscle activation (on the basis of clinical evaluation by [name] and her team) to use the proposed wearable EMG/IMU sensor for the purposes of this study.

- Evidence of at least partial voluntary head movement in at least 2 degrees of freedom (Individual differences in providing controlled movements of the head in various degrees of freedom due to their disease or trauma is not only acceptable but desirable).

- Sufficient stamina and developmental maturity (on the basis of clinical evaluation by [name]) to attend to the approximately 1-hour protocol outlined in Aims 1 and 3 without excess fatigue or distraction.

- Availability for at least 3-4 testing sessions over the study period.

- No medical or safety restrictions of active head and neck movement (as determined by [name] in consultation with her clinical team).

- Clinical evidence of preserved cognition by a score of 0 or 1 on NIHSS Consciousness and Communication item.

- Ability to voluntarily blink eyes or raise eyebrows on command.

## Exclusion criteria:

- Non-English speaker.

- Inability to follow simple instructions in English.

- Medical history of musculoskeletal conditions (arthritis, spondylosis, etc.) that severely limit head movement or causes pain on head movement.

- Restricted active or passive rotation of head and neck resulting from unstable vertebral, spinal cord, or nerve roots that places the subject at risk.

- Medical history of cardiac or respiratory complications, or similar disorders that would severely reduce stamina and/or place the subject at risk for conducting the different motor activities.

- Skin disorders that result in open lesions or hyper-sensitive/fragile skin on the forehead, preventing the use of medical-grade adhesive tapes to secure the sensors to the skin.

- Unable to provide informed consent in English.

CONTROLS

Inclusion Criteria:

- Adults and Children; >8 y.o.

- Male or Female.

- All participants will be: (a) able to spell, (b) able to follow 2-3 step directions, (c) have functional vision sufficient to read 40 point text.

- No history of communication disorders.

- No history of neurological disorders affecting speech or head movement.

### Exclusion Criteria:

- Non-English speaker.
- Inability to follow simple instructions in English.
- Restricted ROM of the head or neck.
- Pain with head movement.

- Medical history of cardiac or respiratory complications, or disorders that would place the subject at risk for conducting the different motor activities.

- Skin disorders that result in open lesions or hyper-sensitive/fragile skin on the forehead, preventing the use of medical-grade adhesive tapes to secure the sensors to the skin.

- Unable to provide informed consent in English.

## **Recruitment Process**

Participants with SPI meeting the Inclusion/Exclusion criteria will be recruited primarily through referrals from [name] and [name] who provide a primary point of contact for AAC evaluation and intervention for children and adults with SPI. Control subjects meeting the Inclusion/Exclusion criteria will be recruited primarily through posting and flyers in the Boston University region in Boston, MA (Downtown and Mid-town Campuses in Boston) and in the immediate area around Altec, Inc. at local cafes, shopping malls, and fitness centers.

#### **Informed Consent**

All subjects will be properly informed of the purpose of the study by the research team. The prospective subjects will have the opportunity to read an IRB-approved informed consent form outlining the experimental procedures, risks, and rights as a human subject and see the actual equipment demonstrated to them. Written consent will be obtained from adults, written parental consent and assent will be obtained from pediatric participants. A signed and dated copy of the consent form will be provided to each subject/parent. All researchers involved in the experimental procedures and analysis of human subject data as outlined in this proposal have training certification on file and are familiar with the appropriate Federal guidelines regarding the use of human subjects for research.

### Potential Risk and Protection against Risk

The identifiable risks, which fall into the category of less than minimal physical risks, are described below.

1. The primary medical risk includes possible irritation to the skin caused by securing and removing the sensors from the skin. The risk is comparable to having a Band-Aid on the skin and peeling it off. To mitigate this risk, the skin will be inspected before and following removal of the sensors and wiped using an alcohol swab. An over-the-counter skin moisturizing cream will be available should the subject feel any irritation or dryness at the sensor locations.

2. Some temporary tiredness and muscle fatigue may result in the participants with SPI from performing the head movement activities. This risk is similar to a light exercise session and is a natural consequence of using one's muscles in daily life, or using a head mounted control for AAC, and will be minimized by offering frequent rest periods.

3. Risks of injury or discomfort to the cervical spine caused by active movement of the head and neck for persons with SPI from head or neck injuries such as traumatic high-level spinal cord injury will warrant special consideration. SPIs in the acute phase of recovery following a spinal cord injury will be excluded as well as those who are immobilized using an orthotic or traction to minimize head movement will also be excluded. All prospective subjects with spinal cord injury regardless of stage of recovery will be careful screened by [name] and her medical team so that all prospective subjects are medically cleared to perform active head and neck movements of the kind described in this study.

4. The risk of electric shock is highly unlikely and greatly minimized because the sensors used in this study are wireless and designed to completely isolate the subject from sources of electrical current. These circuits ensure subject safety in compliance with United States and European EN60601 safety standards for medical instrumentation. They are in compliance with CE and FDA Medical Device Standards for allowable leakage currents.

5. Although unlikely, a breach in the secure network at our facilities could cause video or research data to become publicly available. All data will be kept on secure servers and will be shared with collaborators only through secured connections. All data will be coded for safety.

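### Do the differing age limits, and an acute spinal cord injury exclusion found only in the risk section, leave eligibility unsettled?

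*Combined protocol and SAP*

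**What the plan says.** **Age.** Involvement of Human Subjects states the limit twice as 8 or older: once for all participants, controls included, and once for children who need augmentative and alternative communication (AAC). Under Inclusion/Exclusion Criteria, the SPI list and the control list each state it as over 8.

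**Spinal cord injury.** Item 3 of Potential Risk and Protection against Risk states that "SPIs in the acute phase of recovery following a spinal cord injury will be excluded as well as those who are immobilized" by an orthotic or traction. It goes on: "All prospective subjects with spinal cord injury regardless of stage of recovery will be careful screened by" a named clinician with medical colleagues. The purpose of this screening is given as "so that all prospective subjects are medically cleared to perform active head and neck movements of the kind described in this study".

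The SPI inclusion list gives, among its qualifying causes, "acquired SPI disabilities resulting from high spinal cord injury", with no stage of recovery attached. The same list requires "No medical or safety restrictions of active head and neck movement" and "Evidence of at least partial voluntary head movement in at least 2 degrees of freedom". The SPI exclusion list contains "Restricted active or passive rotation of head and neck resulting from unstable vertebral, spinal cord, or nerve roots that places the subject at risk" and "Medical history of cardiac or respiratory complications, or similar disorders that would severely reduce stamina and/or place the subject at risk".

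**Recruitment.** Recruitment Process says that both groups are recruited as people who meet the inclusion and exclusion criteria.

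**The concern.** Because recruitment refers to the criteria, the two lists are the text a screener would naturally use. Two things could then go wrong.

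First, if age is recorded in completed years, one screener could accept an 8-year-old under the general section while another refuses the same child under the list. Reading more of the protocol does not help, since no statement is given precedence.

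Second, a candidate in the acute phase after spinal cord injury who has been medically cleared could satisfy every listed item, although the risk section excludes that person. The rule is there to protect the cervical spine, so a missed exclusion would be a safety matter as well as an editorial one.

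**Working it through.** There is no sample size, power or error rate to reproduce here, so the check is a comparison of texts with some counting.

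**Step 1: the age statements.** Two of four say 8 or older (both in Involvement of Human Subjects) and two of four say over 8 (the SPI and control lists). The size of the difference depends on how age is measured, which the protocol does not say:

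- Exact age: the limits differ only on the eighth birthday, which is 1 day.
- Completed years (an assumption): they differ from the eighth birthday to the day before the ninth, which is 365 days, or 366 with a leap day.

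The lists show a plain greater-than sign, whereas the general section shows the combined symbol. An underlined greater-than sign that lost its underline when the file was converted to text would look the same, so the mismatch may not exist in the source. That is possible but not shown.

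Under either limit, the functional conditions in the lists (spelling, following 2-3 step directions, reading 40 point text) apply equally.

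**Step 2: item 3 against the SPI list.** Item 3 gives three protections.

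| Protection in item 3 | Counterpart in the SPI list |
|---|---|
| Medical clearance of every spinal cord injury candidate | Direct: no medical or safety restriction on head and neck movement |
| Exclusion if immobilised by orthotic or traction | Not named; covered in effect by the same item and by the voluntary head movement item |
| Exclusion in the acute phase | None |

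One has a direct counterpart, one is covered in effect and one has none.

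**Step 3: the rest of the SPI list.** It has 11 inclusion + 7 exclusion = 18 items. At least 4 of the 18 bear on the same risk: safety restrictions, voluntary head movement, unstable spine, and cardiac, respiratory or similar disorders. Adding the items on head control, stamina and limiting or painful musculoskeletal conditions gives 4 + 3 = 7. These may remove some acute candidates; the protocol gives no frequencies, so how many is unknown. None of the 18 states a rule by stage of recovery.

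**Step 4: do the two texts conflict on spinal cord injury?** Naming high spinal cord injury as a cause does not say that every stage qualifies. Item 3 excludes the acute phase outright. Its next sentence, which screens candidates at any stage, can be read with the exclusion: everyone is screened, and the exclusion applies as well. Applying the whole protocol therefore gives one answer for the acute-phase candidate.

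**Step 5: effect on the analysis.** The analysis text under Alternatives to Participation adopts a single-subject approach in which each participant's performance on the individualised keyboard is compared with that person's own performance on the QWERTY keyboard. No planned summary is split by age or by time since injury. Admitting or refusing a marginal candidate changes who is studied, but not how the two keyboards are compared within a person.

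**The case for a change.** The strongest case for a change is that a safety exclusion belongs where screeners look, and that clearance cannot stand in for it, because item 3 states the stage rule in addition to clearance. The age statements do disagree as written, they concern the youngest participants, and the protocol itself treats children as a vulnerable group. The remedy would be a short wording amendment.

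Part of this stands. The age wording differs, the stage rule is missing from the list, and the term acute phase is not defined anywhere, so repeating it in the list would not by itself make screeners consistent.

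The practical consequence depends on a screener who sees only the lists, and the protocol describes nobody in that position for spinal cord injury. SPI participants come mainly by referral from people who provide AAC evaluation. The list itself leaves head control, stamina and movement safety to clinical evaluation or determination, and a medical team must clear every spinal cord injury candidate. An amendment would align or repeat wording the protocol already contains, at the cost of ethics review, and would alter no procedure or analysis.

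**Conclusion.** No change to the plan is called for. The spinal cord injury half is a detail left out of a list but stated elsewhere in the same protocol; 1 of 3 protections lacks a counterpart in the SPI list, and that one is explicit in the risk section. The age half is a clerical disagreement of 2 statements against 2, worth one day on exact age and up to 366 days per child on completed years.

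This rests on two assumptions: that the study team follows the whole protocol and not the lists alone, and that the medical clearance in item 3 is carried out as written. The protocol gives no counts of 8-year-olds or acute-phase candidates, so the number at the margin cannot be estimated.

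The age statements, and the list and item 3, are for the sponsor to reconcile whenever the text is next revised. Nothing here says which age limit or which clinical rule is right.

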# **Vulnerable Subjects**

Children and subjects with SPI can be considered as vulnerable populations and we will abide by the federal regulations in effect for inclusion of such research participants as overseen by IRB review and approval.

# Confidentiality

The file linking subjects' name to codes will be in paper form and will be stored in a locked file cabinet along with signed consent forms. All sensor data will be password protected on lab servers. Access will only be available to those working on the project. For cases where data are shared between clinical collaborators and Altec, Inc. only de-identified, raw data will be shared. This removes risk that a patient's privacy may be compromised. In case the subject gives explicit permission to take photo and video recordings during the experiment these will be stored in the password protected project folder on the lab servers. All digital data will be identified only by subject codes. To help us protect privacy, this project also has a certificate of Confidentiality from the Federal Government.

# **Potential Benefits to the Subjects**

There are no anticipated benefits for subjects in this study aside from the potential benefits to the population of individuals with SPI in need of AAC devices for communication if our results lead to a more adaptable and optimized AAC system.

# **Alternatives to Participation**

This study does not involve medical diagnostics or treatments for which alternatives should be offered.

A series of signal acquisition and processing software will be developed to collect and analyze sEMG and IMU signals from wearable sensors to develop algorithms for person-centric AAC cursor control, which will then serve to train machine learning algorithms to achieve an individualized AAC keyboard interface. We will validate these developments to show that an individualized keyboard interface can provide improved communication performance compared to a generic (QWERTY) keyboard interface.

The analyses of sEMG and IMU data will be guided by our knowledge of sensor and signal processing solutions for human machine interfaces for preliminary prototype studies and early development of concepts rather than to prove efficacy. We purposely want to collect data from a diverse group to be able to capture a range of movement limitations so that we have a variety of potential "adaptations" the interface can make. A *single-subject design approach will therefore be adopted to evaluate these different, personalized adaptations.* For this reason, data analysis will be conducted across participants to compare individualized AAC device performance to generic (QWERTY) AAC device performance.

Data analysis will follow the U.S. Department of Education standards for single-subject statistical designs as each participant engages in a series of transcription (scripted) tasks to examine user-specific communication performance between our individualized AAC device and a generic (QWERTY) AAC device. Participant communication performance will collected within a single session for each device; the QWERTY keyboard will be analyzed in the second session (Day 2) to serve as a reference for communication performance (i.e., due to widespread familiarity in using the QWERTY keyboard for mobile device communication) once participants are familiar with the sEMG/IMU access method.

The change in level (mean) and variability (standard deviation) of communication performance will be evaluated via metrics of information transfer rate (bits/min), movement time (sec), target selection accuracy (%), movement variability (unitless), and perceived usability for each participant across the two conditions. Average level and variability metrics will be reported for each metric to understand the effects of using an individualized keyboard interface compared to a generic one.

The output of these tasks will be a novel body-worn sensor-based access method, an access assessment test protocol and individualized keyboard interfaces that provide more accurate and accessible AAC over generic interfaces for individuals with SPI.

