## **Specific Aims**

A series of experiments will be performed where control subjects and participants with SPI will be asked to perform head movements and eyeblinks to control the movement of a cursor and the selection of targets on a computer or tablet screen while IMU and sEMG signals are recorded from a sensor placed on the participants' forehead. These experiments will demonstrate that a novel sEMG/IMU-based access method is uniquely capable of characterizing subject-specific variations in movement capabilities in a heterogeneous sample of individuals with SPI to inform the adaptation of an AAC keyboard interface that accommodates residual motor function unique to each user. Specifically, sEMG and IMU signals during head movement and eyeblinks will be translated into repeatable cursor control and target selection that replicate subject-specific movement capabilities. This information will be used to adapt the configuration, orientation, and layout of an AAC orthographic keyboard interface to accommodate the head movement characteristics unique to each subject. The newly developed sEMG/IMU-based models and personalized keyboard interface will be tested to demonstrate that this new access method improves AAC performance when compared to communicating on a generic cursor-to-text AAC interface that uses the same configuration but is not optimized for the individual.

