# Protocol

The experiments require the subjects to utilize head motion to move a cursor on a computer or tablet screen interface. These interfaces will be of two general kinds: an interface that affords us the opportunity to assess generic cursor sensor control for targets located at different orientations and distances; and an orthographic interface where letters are arranged in either a standard (QWERTY) keyboard configuration or an optimized configuration specific to their individual control capabilities. During all experiments, participants will be seated in front of a monitor or tablet and asked to move a cursor appearing on the screen based on data extracted from a wireless Trigno Avanti (Delsys, Inc.) sensor worn on their forehead. When the cursor reaches the target, the subject must select the target by contracting their facial muscle (i.e.: via sEMG signals from either eye blinking or raising their eyebrows).

In some tasks, letters will be highlighted in the appropriate sequence to spell words presented to the subject. The selection and capture of the targets by the subject will be achieved by blinking or raising their eyebrow while the cursor is hovering at or near the target. In other tasks, participants will be asked to spell a series of words presented to them on the computer interface by moving the cursor with the aid of the head mounted IMU and select the target with the aid of the measured sEMG activity. The number of sentences will be arranged in consultation with our clinical collaborators so that the procedures can be completed within a reasonable timeframe.

Additional data acquisition during these experiments may include standard video recordings to assist in post-processing interpretation of results; and user-rated report of fatigue, effort, perceived benefit, ease of use or satisfaction through a brief Likert-type questionnaire.

Each session should require 1-3 hours over 1-2 sessions (depending on subject stamina) with rest periods provided at least every 10 minutes to avoid fatigue or lack of attentiveness.

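### Could the individualized-versus-QWERTY averages mix healthy controls into a result meant for individuals with SPI?

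*Combined protocol and SAP*

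**What the plan says.** Specific Aims introduces the work with both groups: "A series of experiments will be performed where control subjects and participants with SPI will be asked to perform head movements and eyeblinks". The Protocol section describes two kinds of interface. One tests general cursor control; the other is a spelling interface in which "letters are arranged in either a standard (QWERTY) keyboard configuration or an optimized configuration specific to their individual control capabilities".

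Controls have their own eligibility list, which also uses the word *participants* ("All participants will be: (a) able to spell"). It requires "No history of neurological disorders affecting speech or head movement" and lists "Restricted ROM of the head or neck" as an exclusion.

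The data analysis text, printed under Alternatives to Participation, adopts a single-subject design because a diverse sample is wanted. It then states: "For this reason, data analysis will be conducted across participants to compare individualized AAC device performance to generic (QWERTY) AAC device performance". Level (mean) and variability (standard deviation) of five performance measures are evaluated for each participant under the two keyboards, and "Average level and variability metrics will be reported for each metric". The closing sentence describes the project's output as interfaces that "provide more accurate and accessible AAC over generic interfaces for individuals with SPI".

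**The concern.** Two groups are enrolled, the comparison runs over participants without saying which, and the output is stated for one group only. *Participants* cannot be assumed to mean SPI, since the control criteria use it too. No sentence expressly keeps controls away from the keyboard task.

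The groups also differ on the feature that matters. The individualized keyboard is meant to adapt to residual motor function, and controls are selected to have no restriction of head movement. Their gain or loss relative to QWERTY need not match that of SPI participants. If the two were averaged together, a reader could not attribute the summary to the target population. In the extreme, an apparent benefit could come from controls alone.

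**Working it through.** The documents give no sample size, group split, effect size or standard deviation, so there is no planned figure to reproduce. The check has two parts: what pooling would do if it happened, and whether the text calls for it.

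**What pooling would do.** Let c be the share of controls in the average and f the control effect as a multiple of the SPI effect. Both are assumptions. Then

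pooled mean / SPI mean = (1 − c) + c × f

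| c (assumed) | f = 0 | f = 1 | f = 1.5 |
|---|---|---|---|
| 0.25 | 0.75 + 0 = 0.75 | 0.75 + 0.25 = 1.00 | 0.75 + 0.375 = 1.125 |
| 0.50 | 0.50 + 0 = 0.50 | 0.50 + 0.50 = 1.00 | 0.50 + 0.75 = 1.25 |
| 2/3 | 0.33 + 0 = 0.33 | 0.33 + 0.67 = 1.00 | 0.33 + 1.00 = 1.33 |

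The ratio is 1 only if c = 0 or f = 1. If SPI participants gained nothing and controls gained 1 unit, the pooled mean would equal c. These are properties of any weighted mean of two groups. They show that pooling could matter, not that it is planned.

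**Whether the text calls for pooling.**

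1. *The sentence on the comparison.* It opens by referring back to its reason: a diverse sample, a range of movement limitations, and the different adaptations that result. People excluded for restricted head or neck motion cannot supply that range. Specific Aims likewise links the keyboard adaptation to a heterogeneous SPI sample.
2. *Sessions.* Each keyboard is assessed within one session, with QWERTY on Day 2, so the comparison needs at least two. Availability for 3-4 sessions is asked only of SPI participants, as is the stamina for Aims 1 and 3. The control criteria contain neither. This is suggestive only, because the Protocol section allows 1-2 sessions for subjects generally.
3. *The sentences that seem to include controls.* The one in Specific Aims concerns head movements and eyeblinks for cursor control and target selection, not the keyboard comparison. The one in Protocol lists interfaces without saying that each group uses both. The control list shows that *participants* can cover controls, not that it does so in the analysis text.
4. *The averages.* Level and variability are evaluated for each participant. The next sentence, on reporting averages, can mean those per-person values or a mean over people. Under the first reading nothing is pooled. Under the second, the per-person results still allow an SPI-only summary.
5. *Use of the result.* The analysis is described as early development and not proof of efficacy. No hypothesis test, threshold or go/no-go rule depends on a group mean. The closing sentence about SPI lists deliverables and is not tied to a particular average.

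**The case for a change.** The strongest case for a change is that the population of the conclusion is written down and the population of the supporting summary is not. Specific Aims writes *participants with SPI* when it means that group; the analysis text does not. The passage on movement limitations explains why varied data are collected and does not define an analysis set. The same section also speaks of validating the individualized keyboard against QWERTY, and even a descriptive summary should have a named population. One sentence would settle it at no cost in data.

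Much of this stands. The analysis set is unwritten, the session argument is not conclusive, and SPI-only is an inference from context. What does not stand is the step from an unnamed group to a misleading result. That step needs controls to complete both keyboards, the averages to be taken over people, the two groups to be merged, and no split by group to be shown. The plan states none of the last three, and whether controls complete both keyboards is left open.

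There is also a limit on what can be read. Some text was not available for review, including a part just before Specific Aims, and the eligibility criteria refer to numbered aims that do not appear in the text at hand. The allocation of groups to aims may be given there.

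**Conclusion.** No change to the plan follows. The gap is one of missing detail: the text does not say whether controls do the keyboard comparison or whether averages are given by group. An analyst would sensibly summarize SPI participants, with any control results shown separately, and the per-participant evaluation makes that possible without new data.

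No bias in a stated result is shown. The range of 0.33 to 1.33 times the SPI mean rests entirely on assumed control shares and control effects, and applies only to a pooled mean that the plan does not specify. The conclusion assumes that per-participant results are kept by group, as the separate eligibility lists make natural, and that the average serves as description in early development work. It would have to be reconsidered if a test or decision rule were attached to a mean over both groups.
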